### **8.8 Premature termination of the study**

Based on the absence of risk associated with using internet-based interventions in treatment – which have been used in Dutch outpatient treatment for over ten years, without any incidents – we expect that there will be no reason to expect that the study has to be terminated due to detrimental effects of the intervention.

This study is financed for two years. If the intended number of participants has not been reached after two years and if no additional financing has been found, the study will be terminated, even if the intended N has not been reached. In that case, the data from the already enrolled participants will still be collected. If the study has to be terminated before the desired number of participants is included, analyses will be conducted with the available quantitative and qualitative data of the participants that did complete the study.

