#### 4.4 Sample size calculation

This sample size calculation is conservatively based on the ability to detect at least a moderate effect of Cohen's  $d = .50$  on the primary outcomes at follow-up (T3). A power analysis was conducted with G\*power. The analysis was conducted with a moderate effect size of 0.5, a  $\beta$ -power of .8, a p-value of 5%, and an independent two-sided t-test as method of analysis. This analysis showed that 64 patients need to be included in each condition. This means that a total of 128 patients needs to be included. Accounting for a drop-out of 20%, the goal for inclusion is set at a total of 154 patients. It is important to note that participants in the experimental condition are considered as a 'drop-out' when they don't fill out the questionnaires at all measuring moments, not when they stop using the intervention. In other words: patients can stop using the intervention. In other words: patients can stop using the intervention, but can still complete their participation in the study if they fill out all questionnaires. Adherence to the intervention is not the same as drop-out from the study, since it is a different concept. The main reason for this is that earlier research has shown that patients often stop using these interventions before all lessons are completed, so it is not realistic to expect that all patients fully complete the intervention. In order to account for this, the number of completed lessons will be included as a moderator for effectiveness in the analyses to investigate whether adherence is related to effectiveness. Additionally, a sub-goal of this study is to determine whether engagement is a predictor of adherence and effectiveness to incorporate non-adherence to the intervention in the study. The intended 154 patients will be included at four different organizations that all have multiple forensic outpatient clinics.

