## 10. STATISTICAL ANALYSIS

### 10.1 Primary study parameter(s)

Data will be analysed using IBM SPSS software (version 24.0) and significance was accepted at 0.05 or lower. Analyses will be done on intention to treat (ITT) basis.

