#### ***Research objective 1: Self-efficacy, treatment readiness, and aggression***

To identify whether there are changes in dependent variables between the experimental and control group on baseline (T0), during the intervention (T1), post-intervention (T2) and follow-up assessment (T3), multilevel repeated-measures linear mixed models will be used. This analysis method accounts for autocorrelation within participants and missing data. Time and group will be used as fixed factors, along with their interactions, and participants are modelled as random factor. Interaction effects will be studied to identify whether the changes over time differed between groups. Main effects for time will be used to investigate whether the scores of all participants changed over time. In order to provide more insight into the main findings, Least-significant difference (LSD) post-hoc independent t-tests with Bonferroni correction will be performed to test for significant between-group differences and changes over time per group.

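### If enrolment stops short of target, section 8.8 narrows the analysis set from all randomised patients to study completers, in conflict with the intention-to-treat basis of section 10.1

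*Combined protocol and SAP*

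**What the plan says.** Section 10.1 states without exception: "Analyses will be done on intention to treat (ITT) basis". For the three self-report outcomes, the text on research objective 1 says that "multilevel repeated-measures linear mixed models will be used", and adds: "This analysis method accounts for autocorrelation within participants and missing data".

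Section 8.8 covers a shortfall in recruitment. It notes "This study is financed for two years" and provides that, without new funding, the study ends even if the target has not been met. It continues: "In that case, the data from the already enrolled participants will still be collected". Its last sentence sets the analysis: "If the study has to be terminated before the desired number of participants is included", then "analyses will be conducted with the available quantitative and qualitative data of the participants that did complete the study".

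Two other sections bear on what completing means:

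- Section 4.4 says that a patient who stops the intervention "can still complete their participation in the study if they fill out all questionnaires". It counts as a drop-out anyone who does not answer at every measuring moment.
- Section 8.6 counts as a drop-out anyone who stops answering before the study ends.

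**The concern.** The plan has two rules for who is analysed, and which one applies depends on whether enrolment reached 154. That has nothing to do with treatment. Under 10.1 a patient who answered at T0 and T1 and then stopped still contributes. Under 8.8 the same patient is left out.

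Completing is decided after randomisation, and patients and therapists know the allocation. If the patients who stop answering differ between the arms, the comparison among completers is no longer the randomised one. Nothing in 8.8 explains the restriction, and its own statement that data collection continues for enrolled patients removes any practical need for it. The situation is foreseeable: 8.8 plans for it, and section 4.5 calls inclusion in forensic care potentially problematic.

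**Working it through.** **Size of the affected group.** Section 4.4 assumes d = 0.5, a two-sided t-test at 5%, power 0.80 and 20% drop-out. The t-test solution is 63.77, so 64 per arm and 128 in total. Then 128 × 1.2 = 153.6, which gives the stated 154. On the plan's own drop-out assumption, a completers-only set leaves out about one randomised patient in five, whatever number is enrolled.

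**Who is left out.**

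| Patient | Section 10.1 | 8.8, completing as in 4.4 | 8.8, drop-out as in 8.6 |
|---|---|---|---|
| Stops after T0, T1 or T2 | included | left out | left out |
| Misses T1 only, has T3 | included | left out | kept |

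The first row is the same under both definitions. The second is not, because 4.4 and 8.6 differ.

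**How large the second row could be under 4.4.** Assume that 20% of patients miss at least one of T1 to T3, independently across visits.

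- Missing per visit: 1 - 0.8^(1/3) = 0.072.
- Share with a T3 score: 0.8^(1/3) = 0.928.
- Share with T3 who are not completers: 0.928 - 0.800 = 0.128, about 13%.

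Under 8.6, or if all missingness is permanent drop-out, this share is 0%.

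**Bias among completers.** The documents give no visit correlations and no drop-out mechanism, so these are assumptions: unit variance, correlations falling from 0.6 between adjacent visits to 0.45 between T0 and T3, no true effect, and permanent drop-out. Where drop-out depends on the score, patients with a poorer last observed score leave more often, with the stated log-odds per SD. A positive difference favours the intervention.

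| Drop-out mechanism | Completing, experimental / control | Completers' T3 difference (SD) |
|---|---|---|
| Experimental arm only, log-odds 1 | 75% / 81% | +0.13 |
| Experimental arm only, log-odds 0.5 | 75% / 81% | +0.07 |
| Both arms, log-odds 1 | 75% / 81% | +0.03 |
| Both arms, log-odds 1 | 78% / 78% | 0.00 |
| Random in both arms | 75% / 81% | 0.00 |
| Control arm only, log-odds 1 | 75% / 81% | -0.09 |
| Control arm only, log-odds 1 | 81% / 75% | -0.13 |

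A likelihood estimate from all observed visits is 0.00, within simulation error, in every row. It is unbiased here because drop-out depends only on observed scores and the covariance is modelled correctly.

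A separate simulation with a true T3 effect of 0.50, correlation 0.6 and 20% drop-out per arm after T1 agrees. With drop-out driven by a poor T1 score in the experimental arm only, completers give 0.62 and the likelihood estimate 0.50. With the same mechanism in both arms, both give 0.50.

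**The case against.** The best defence is that 8.8 is an administrative section. It never says only or instead of 10.1, it refers to available data, and it keeps collecting from enrolled patients. Its purpose may simply be that a shortfall will not cancel the analysis. That may be the intent, but the sentence ties the available data to participants who completed, and no section reconciles this with 10.1. If the broader meaning is intended, the same one-sentence correction is needed.

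Four stronger readings are tempting, and the documents do not support them.

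- *The mixed model is replaced.* Section 8.8 names no model, and one could still be fitted to completers. What changes is the analysis set and the use of partial data.
- *Patients with a recorded T3 score are certainly discarded.* This follows from the wording in 4.4 but not from 8.6, so the 13% is conditional on one of two definitions.
- *The rule flatters the intervention.* No section says in which arm drop-out would depend on the score. The bias can take either sign or be zero.
- *The rule costs precision in a sample that is already small.* With 60 per arm and no true effect, simulation of the +0.13 scenario gave the same SD, 0.206, for the completers' estimate and the likelihood estimate. The case rests on bias and on the integrity of the analysis set.

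The rule also applies only if recruitment falls short and no further financing is found, and section 4.5 expects the target to be met. That limits the weight of the point. It does not remove the contradiction.

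**Conclusion.** The conflict is real and lies in the text: 10.1 analyses all randomised patients, while 8.8, on early termination, analyses those who completed. Patients who stop answering after T0, T1 or T2 are left out under either definition of drop-out. Those who miss one visit before T3 but have T3 are left out only under 4.4, about 13% if 20% miss at least one visit independently.

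Under the stated assumptions the bias in the T3 difference ranges from about -0.13 to +0.13 SD. The extreme is about a quarter of the design effect (0.13 / 0.5 = 0.26). It needs score-dependent drop-out in one arm only, which is plausible without blinding but not shown by the documents. The correction should be made because it costs almost nothing, and it should be settled before outcome data are seen.

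**What to change.** Replace the last sentence of 8.8 with: *If recruitment stops early, follow-up of enrolled participants continues as planned and the analysis is that of section 10.1: all randomised participants, as randomised, with all available assessments.* Any completers analysis should be labelled as a sensitivity analysis and should say which definition of completing it uses, since 4.4 and 8.6 differ.

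The sentence should not promise that every randomised patient will finish all assessments, because section 8.5 allows withdrawal at any time. Section 8.7, which excludes patients who leave treatment entirely, conflicts with intention to treat whether or not enrolment stops early. It must be reconciled with 10.1 separately, as this change to 8.8 does not resolve it.

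The cost is one sentence, with no extra patients, visits or data.

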## 9. SAFETY REPORTING

### 9.1 Temporary halt for reasons of subject safety

In accordance to section 10, subsection 4, of the WMO, the sponsor will suspend the study if there is sufficient ground that continuation of the study will jeopardise subject health or safety. The sponsor will notify the accredited METC without undue delay of a temporary halt including the reason for such an action. The study will be suspended pending a further positive decision by the accredited METC. The investigator will take care that all subjects are kept informed.

### 9.2 AEs, SAEs and SUSARs

#### 9.2.1 Adverse events (AEs)

Adverse events are defined as any undesirable experience occurring to a subject during the study, whether or not considered related to the study. All adverse events reported spontaneously by the subject or observed by the investigator or his staff will be recorded. All involved therapists will be required to report adverse events to the main researcher, who will record them.

#### 9.2.2 Serious adverse events (SAEs)

A serious adverse event is any untoward medical occurrence or effect that

- results in death;
- is life threatening (at the time of the event);
- requires hospitalisation or prolongation of existing inpatients' hospitalisation;
- results in persistent or significant disability or incapacity;
- is a congenital anomaly or birth defect; or
- any other important medical event that did not result in any of the outcomes listed above due to medical or surgical intervention but could have been based upon appropriate judgement by the investigator.

An elective hospital admission will not be considered as a serious adverse event.

If SAEs occur, the sponsor will report the SAEs through the web portal *ToetsingOnline* to the accredited METC that approved the protocol, within 7 days of first knowledge for SAEs that result in death or are life threatening followed by a period of maximum of 8 days to complete the initial preliminary report. All other SAEs will be reported within a period of maximum 15 days after the sponsor has first knowledge of the serious adverse events.

SAEs due to the internet-based intervention are not expected because it does not influence the physical state of the participant in any way.

If any SAEs occur, they will be reported by the sponsor the web portal *ToetsingOnline* to the accredited METC that approved the protocol, within 7 days of first knowledge for SAEs that result in death or are life threatening followed by a period of maximum of 8 days to complete the initial preliminary report. All other SAEs will be reported within a period of maximum 15 days after the sponsor has first knowledge of the serious adverse events.

### **9.3 Annual safety report**

Not applicable.

### **9.4 Follow-up of adverse events**

All AEs will be followed until they have abated, or until a stable situation has been reached. Depending on the event, follow up may require additional tests or medical procedures as indicated, and/or referral to the general physician or a medical specialist. SAEs need to be reported till end of study within the Netherlands, as defined in the protocol

### **9.5 Data Safety Monitoring Board (DSMB) / Safety Committee**

Not applicable.

## 10. STATISTICAL ANALYSIS

### 10.1 Primary study parameter(s)

Data will be analysed using IBM SPSS software (version 24.0) and significance was accepted at 0.05 or lower. Analyses will be done on intention to treat (ITT) basis.

#### ***Research objective 1: Self-efficacy, treatment readiness, and aggression***

To identify whether there are changes in dependent variables between the experimental and control group on baseline (T0), during the intervention (T1), post-intervention (T2) and follow-up assessment (T3), multilevel repeated-measures linear mixed models will be used. This analysis method accounts for autocorrelation within participants and missing data. Time and group will be used as fixed factors, along with their interactions, and participants are modelled as random factor. Interaction effects will be studied to identify whether the changes over time differed between groups. Main effects for time will be used to investigate whether the scores of all participants changed over time. In order to provide more insight into the main findings, Least-significant difference (LSD) post-hoc independent t-tests with Bonferroni correction will be performed to test for significant between-group differences and changes over time per group.

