### ***Research objective 3: Dynamic risk factors***

To determine if there is more improvement on dynamic risk factors as measured by a risk assessment instrument in patients who received the internet-based intervention 'Aggression' as an addition to TAU, compared to those who only receive TAU. For this research objectives, the same analysis as for research objective 1 will be used.

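### The T3 comparison is not adjusted for the baseline score and the deciding T3 contrast is not named; a baseline-adjusted contrast would be more efficient at almost no cost

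*Combined protocol and SAP*

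**What the plan says.** Section 10.1 (Research objective 1) treats T0, T1, T2 and T3 as time points of the dependent variable in a linear mixed model: "Time and group will be used as fixed factors, along with their interactions, and participants are modelled as random factor". The interaction is used to see whether change over time differs between the groups. To expand on the main findings, "post-hoc independent t-tests with Bonferroni correction will be performed to test for significant between-group differences". Section 10 names no baseline covariate and no constraint of equal T0 means.

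The part of 10.1 on determining effectiveness bases its strongest conclusions on T3, but does not say whether the interaction, a T3-minus-T0 contrast or the T3 t-test supplies the answer. For the FARE, section 10.2 (Research objective 3) says that "the same analysis as for research objective 1 will be used".

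Section 4.4 sizes the trial on "an independent two-sided t-test as method of analysis", again without a baseline term.

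**The concern.** If T0 is measured before allocation, the two arms have the same expected T0 mean by design. A model with time, group and their interaction estimates those two means separately and so sets that knowledge aside. Only two T3 contrasts then follow: the group difference at T3, which ignores T0, and the T3-minus-T0 interaction contrast, which compares change scores. Neither is adjusted for T0.

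Two things are at stake. One is precision that the trial could have from data it already collects. The other is a T3 conclusion that can depend on an unstated choice between two contrasts, which a chance difference at T0 pushes in opposite directions.

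**Working it through.** **Inputs from section 4.4.** "The analysis was conducted with a moderate effect size of 0.5"; "power of .8, a p-value of 5"%; a two-sided independent t-test; "64 patients need to be included in each condition".

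**Assumptions.** The SD is 1 at both T0 and T3, data are complete, and r is the T0–T3 correlation. The documents give no value for r, so a range of 0.2 to 0.7 is shown. All tests are at two-sided 5% before any Bonferroni step.

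**Reproducing the plan's figure.** The noncentral t distribution with d = 0.5, 80% power and two-sided 5% gives 63.77, so 64 per arm and 128 in total; power at 64 is 80.1%. The plan then states: "Accounting for a drop-out of 20%, the goal for inclusion is set at a total of 154 patients". This is 128 × 1.2 = 153.6, rounded up. The comparison below uses the 64 per arm on which the plan bases its power.

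**Variance of each T3 contrast, relative to the raw difference (variance 2/n):**
- raw T3 difference: 1
- T3 minus T0: 2(1 − r)
- T0 as covariate, or T0 means constrained equal: 1 − r²

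The adjusted contrast has the smallest variance for any r strictly between 0 and 1. Against raw, 1 − r² < 1. Against change, 2(1 − r) − (1 − r²) = (1 − r)² > 0.

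**Power at 64 per arm.** The effective effect size is 0.5 / √(relative variance). For r = 0.5 the adjusted value is 0.5 / √0.75 = 0.577. For r = 0.3 the change value is 0.5 / √1.4 = 0.423.

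| r | Relative variance, change | Relative variance, adjusted | Power, raw | Power, change | Power, adjusted |
|---|---|---|---|---|---|
| 0.2 | 1.60 | 0.96 | 80% | 60% | 82% |
| 0.3 | 1.40 | 0.91 | 80% | 66% | 84% |
| 0.4 | 1.20 | 0.84 | 80% | 73% | 87% |
| 0.5 | 1.00 | 0.75 | 80% | 80% | 90% |
| 0.6 | 0.80 | 0.64 | 80% | 88% | 94% |
| 0.7 | 0.60 | 0.51 | 80% | 95% | 98% |

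Expressed as sample size, the adjusted contrast needs 59, 49 and 34 per arm for 80% power at r = 0.3, 0.5 and 0.7. The raw test needs 64, and the change contrast needs 89, 64 and 39.

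**Chance imbalance at T0.** With 64 per arm the T0 difference has SD √(2/64) = 0.177, so a 95% range of about ±0.35 SD. An imbalance δ shifts the raw T3 difference by rδ and the change contrast by (r − 1)δ; the adjusted estimate is not shifted. At r = 0.5 and δ = 0.35 the shifts are +0.175 and −0.175 SD, which is 0.175 / 0.5 = 35% of the design effect. Given an imbalance of that size, type I error is about 13% for either unadjusted contrast, and raw-test power at d = 0.5 is 44% or 98% depending on its direction. Averaged over all randomisations, simulated type I error stays close to 5% (4.9% to 5.6%).

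**Does the choice of contrast matter?** In simulated trials with 64 per arm and d = 0.5, the raw and change tests disagreed on significance in about 20% to 27% of trials for r from 0.7 down to 0.3.

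**Does T0 precede allocation?** Section 3.3 and section 8.3 Step 4 place T0 before allocation. Section 8.3 Step 5 places randomisation immediately after consent, with no mention of T0 in between. Section 3.3 also puts T0 in week 12, which Step 5 gives as the week of randomisation, while Step 4 puts T0 in week 11.

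**The case against.** The plan's model is standard and valid. Three stronger readings are tempting, and the documents do not support them.

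- **That T0 is never used as a baseline.** The interaction measures change from T0, and the t-tests are introduced as post-hoc support for the mixed model. T0 is used, but not adjusted for.
- **That the trial loses its planned power.** Section 4.4 is sized on an unadjusted t-test, and that test keeps its nominal 80% before any Bonferroni step. What is forgone is an available gain. It is small at low r (about 2 points at 0.2 and 4 at 0.3), and T3 is 26 weeks after T0, so a low r cannot be excluded. Above r = 0.5 the change contrast already beats the raw test, and at 0.7 it comes within 3 points of the adjusted one. Below 0.5, however, the change contrast does worse than the 80% on which the trial was sized.
- **That chance imbalance biases the result.** Randomisation keeps the unconditional type I error near 5%; the effect is conditional on the imbalance that happens to occur. The absence of stratification by organisation or clinic (section 8.2) adds little, because such strata would not directly balance questionnaire scores.

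The remedy also has a condition. Equal T0 means are guaranteed only if T0 is completed before allocation. In an unblinded trial, a T0 questionnaire answered after the arm is known could be affected by it. For the FARE, the note under Table 1 allows its date to differ from T0.

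What survives all this is that no T0 adjustment is planned, that the deciding T3 contrast is not named, and that an analysis at least as good at every r in the range is available from data already being collected.

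**Conclusion.** The point holds as an efficiency and specification issue. Relative to the raw T3 test, adjusting for T0 adds roughly 2 to 17 percentage points of power for r from 0.2 to 0.7 (10 points at r = 0.5). Relative to the change contrast, it adds about 21 points at r = 0.2 (81.7% against 60.2%) and about 2 at r = 0.7 (97.6% against 95.2%). It also removes the shift from chance T0 imbalance and the ambiguity between two contrasts that can disagree.

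These sizes rest on an assumed r, equal SDs at T0 and T3, complete data, and a 5% level with no Bonferroni step. The ordering of the three contrasts does not depend on the value of r between 0 and 1. The conclusion also depends on T0 preceding allocation, on which the protocol is not consistent.

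**What to change.** 1. In section 10.1, fit T1 to T3 as outcomes with the T0 score and its interaction with time as covariates, or fit a constrained longitudinal model with one common T0 mean and group differences only at T1, T2 and T3.
2. Take the between-group differences at T1, T2 and T3, with 95% CI, from that model in place of the independent t-tests.
3. In the text on determining effectiveness, name the adjusted T3 difference as the contrast that decides the T3 conclusion.
4. Reconcile section 8.3 Step 5 with section 3.3 and Step 4, so that the protocol states unambiguously that T0 is completed before allocation.
5. Apply the same model to the FARE (section 10.2) only where its baseline score predates allocation.

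The cost is one rewritten paragraph, a changed mixed-model specification in SPSS and a clarified order of procedures. It needs no new measurements or patients.

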## SUMMARY

**Rationale:** While internet-based interventions have been used for over ten years in Dutch forensic psychiatric outpatient care, no thorough evaluation study has been conducted yet. Studies on internet-based interventions in other mental healthcare sectors show promising results: they can increase the quality and efficiency of care. However, it is not clear if, why and for whom these interventions work in forensic mental healthcare. It is especially important to study whether these interventions are of added value for this complex patient population, known for its low treatment motivation, co-morbidity and low literacy levels.

**Objective:** The primary objective of this study is to investigate whether the addition of the internet-based intervention 'Aggression' to forensic psychiatric outpatient treatment as usual (TAU) results in better treatment outcomes in terms of self-reported regulatory emotional self-efficacy, treatment readiness, and aggression. Additionally, it is investigated whether the experimental group requires fewer treatment sessions and improves more on dynamic risk factors. Furthermore, to gain more insight into for whom these interventions work, it is investigated whether engagement with the internet-based intervention predicts adherence and effectiveness. Finally, this study aims to explore reasons for the (in)effectiveness of the intervention according to patients and therapists.

**Study design:** To investigate if the use of internet-based interventions is of added value for treatment of forensic psychiatric outpatients, a multicenter, non-blinded, parallel groups, randomized controlled trial design is used. Patients fill out three short self-report questionnaires four times: at baseline, mid-treatment (+6 weeks), post-treatment (+14 weeks) and at follow-up (+26 weeks). Semi-structured interviews with a randomly selected sample of 20 patients from the experimental condition and with all participating therapists are conducted to explain the results of the RCT.

**Study population:** The target group of this study consists of forensic psychiatric outpatients, treated in four Dutch organizations for aggression regulation problems.

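### The primary mixed model names only a random participant effect; unless a residual structure is added and the T3 contrast named, decaying correlation would make the T0–T3 change test too liberal

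*Combined protocol and SAP*

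**What the plan says.** Section 10.1 (Research objective 1) states that "multilevel repeated-measures linear mixed models will be used" and that "Time and group will be used as fixed factors, along with their interactions, and participants are modelled as random factor". It adds: "This analysis method accounts for autocorrelation within participants and missing data". Neither that passage nor the rest of section 10.1 names a residual covariance structure, a random slope, a robust standard error or a degrees-of-freedom method.

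Two routes to a group comparison are described. One is the interaction: "Interaction effects will be studied to identify whether the changes over time differed between groups". The other is a follow-up step in which "post-hoc independent t-tests with Bonferroni correction will be performed to test for significant between-group differences". The significance rule is that "significance was accepted at 0.05 or lower".

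The Summary places the visits at baseline and 6, 14 and 26 weeks later. Section 4.4 sizes the trial on a two-sided independent t-test of the primary outcomes at T3. The subsection on determining effectiveness in section 10.1 makes T3 the visit at which the intervention can be called effective. It does not say which T3 contrast is meant.

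**The concern.** A random participant effect with independent residuals is a compound-symmetry model: one correlation applies to all six pairs of visits, whether they lie 6 or 26 weeks apart. It captures the fact that a patient's scores resemble each other, but not any weakening of that resemblance over time. The sentence about autocorrelation is then met only by a structure that the plan does not name.

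If correlation does weaken, T0 and T3 are the least correlated pair, yet the model gives their difference the average within-patient variance. The test of change to T3 is then too liberal and the test of change to T1 too strict. T3 decides the effectiveness conclusion, so an error there matters more than one at T1. Model-based tests of change within one group carry the same relative error.

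**Working it through.** **Inputs from the plan.** Visits at 0, 6, 14 and 26 weeks (Summary; consistent with baseline in week 11 and visits in weeks 17, 25 and 37 in section 8.3: 17 − 11 = 6, 25 − 11 = 14, 37 − 11 = 26). Standardised effect 0.5, 80% power, two-sided 5%, 64 per arm (section 4.4). No SD is given, so SD = 1.

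**Assumptions.** Within-patient correlations are not given, so a range is used. Data are complete, variances equal across visits, and tests are at an unadjusted 5%.

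**Step 1: the plan's own figure.** A two-sample t-test with effect 0.5 has power 0.8015 at 64 per arm and 0.795 at 63, so 64 is reproduced. That test uses the T3 score alone.

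**Step 2: formulas for change from baseline to visit k.**
- Correct SE of the group difference in change = √[2(1 − ρ₀ₖ) × 2/64].
- Random-intercept SE = √[2(1 − ρ̄) × 2/64], where ρ̄ is the mean of the six pairwise correlations.
- SE ratio = √[(1 − ρ̄)/(1 − ρ₀ₖ)].
- Type I error = 2[1 − Φ(1.96 × ratio)].

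**Step 3: one case in full.** Let correlation be 0.8 over 6 weeks with exponential decay, ρ = 0.8^(gap/6). The gaps 6, 14, 26, 8, 20 and 12 weeks give 0.800, 0.594, 0.380, 0.743, 0.475 and 0.640, so ρ̄ = 3.632/6 = 0.605.
- Model SE, all visits: √(2 × 0.395 × 2/64) = 0.157.
- Correct SE: 0.112 at T1, 0.159 at T2, 0.197 at T3.
- T3 ratio: 0.157/0.197 = 0.80; type I error 2[1 − Φ(1.56)] = 11.8%.

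**Step 4: range.** SE ratio, with type I error in brackets:

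| Assumed correlation | T1 | T2 | T3 |
|---|---|---|---|
| Decay only, 0.9 over 6 weeks | 1.47 (0.4%) | 1.00 (5.1%) | 0.77 (13.2%) |
| Decay only, 0.8 | 1.41 (0.6%) | 0.99 (5.3%) | 0.80 (11.8%) |
| Decay only, 0.6 | 1.28 (1.2%) | 0.97 (5.7%) | 0.86 (9.2%) |
| Decay only, 0.5 | 1.23 (1.6%) | 0.97 (5.8%) | 0.89 (8.2%) |
| 30% stable, 40% decaying (0.8), 30% measurement error | 1.10 (3.1%) | 1.00 (5.1%) | 0.91 (7.3%) |
| 50% stable, 20% decaying (0.9), 30% measurement error | 1.04 (4.2%) | 1.00 (5.0%) | 0.96 (6.0%) |
| Equal at all gaps (0.6) | 1.00 (5.0%) | 1.00 (5.0%) | 1.00 (5.0%) |

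The mildest decaying row has ρ = 0.5 + 0.2 × 0.9^(gap/6), so ρ₀₃ = 0.627 and ρ̄ = 0.657, and the T3 ratio is √(0.343/0.373) = 0.96. A stable patient component without measurement error multiplies every 1 − ρ by the same factor and leaves the ratios unchanged; measurement error is what softens them. If decay runs by visit number rather than weeks (0.8 to 0.5 per step), T3 is 0.79–0.86, T1 1.23–1.14 and T2 0.92–0.93.

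**Step 5: simulation.** With 10,000 trials, 64 per arm and the Step 3 correlations, rejection rates under the null were:
- random-intercept change contrasts: 0.7% at T1, 5.6% at T2, 11.4% at T3;
- T0–T3 contrast with its own variance: 4.9%;
- omnibus time-by-group test: 6.6% (6.0–6.6% over four decaying scenarios);
- between-group difference at T3 alone: 5.0%.

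**The case against.** The strongest reply is that the plan is silent rather than wrong. It calls the model a repeated-measures one and says autocorrelation is handled, so a residual structure alongside the random participant effect may be intended. This stands in part. A reader might infer that the plan forces equal correlations, but the text never says the residuals are independent. It also never names the structure that would make the autocorrelation sentence true.

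A second reply is that unequal visit spacing does not by itself bias any standard error; decay does, and no document reports a correlation. This stands. The last row of the table shows no error under equal correlation, so every figure here is conditional. Short questionnaires plausibly carry measurement error, which moves the result towards the mild end of the range.

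A third reply is that the tests the plan names most clearly are hardly touched. A reader might infer that the T3 test behind the sample size is invalid. The documents do not support that: section 4.4 uses an independent t-test at T3, which held 5.0% in the simulation, and separate t-tests per visit do not use the model covariance. The large inflation arises only if a model-based T0–T3 change contrast decides effectiveness. Section 10.1 permits that reading but does not fix it. This narrows the point and leaves a choice between contrasts with different error rates open until after the data are seen.

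**Conclusion.** The concern holds in conditional form. As written, the model has one named covariance feature, a random participant effect, and without a residual structure this means equal correlation at all gaps. If correlation decays with time, the SE of the group difference in change from T0 to T3 is about 4–23% too small (type I error about 6–13%). The T1 SE is about 4–47% too large (type I error about 0.4–4%), and T2 is about right when decay runs in weeks. The direction was the same in every decaying scenario tried.

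These results rest on assumed correlations, complete data and equal variances. They do not show that the trial's T3 comparison is invalid: the T3-only difference stays near 5% and the omnibus interaction reaches only about 6–7%. The change is worth making because it is cheap and removes an avoidable dependence on an unstated assumption. It is less than a must-fix.

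**What to change.** In section 10.1:
- Replace the random participant intercept with visit as a repeated effect within participant and an unstructured 4×4 residual covariance (SPSS MIXED, REPEATED, UN), fitted by REML with small-sample degrees of freedom. A random intercept adds nothing once the covariance is unstructured.
- If the model does not converge, use a fallback that respects the unequal gaps, such as a continuous-time (spatial power) structure with a random intercept; confirm that the SPSS version named in the plan offers it. Heterogeneous Toeplitz is less suitable, because it gives all adjacent visits one correlation although their gaps are 6, 8 and 12 weeks.
- Name the exact T3 contrast that decides effectiveness: the group difference at T3, or the group difference in change from T0 to T3. Say whether the post-hoc tests come from the model or are separate t-tests.

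The cost is wording. The unstructured matrix has 4 × 5/2 = 10 parameters instead of two, which the planned 154 patients can support. Under decay, intervals for the T0–T3 change widen by about 4–30% (1/0.96 to 1/0.77), which is the correction itself, and those for T1 narrow. If correlations are in fact equal, little is lost.
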